## 4.2 Accountability Procedures

Upon receipt of the study lenses, the Investigator or delegate will conduct an inventory. Designated study staff will provide the study lenses to the subjects in accordance with their randomization schedule. Throughout the study, the Investigator or delegate must maintain records of study treatment dispensation and collection for each subject. This record must be made available to the study monitor for the purposes of verifying the accounting of clinical supplies. Any discrepancies and/or deficiencies between the observed disposition and the written account must be recorded along with an explanation.

It is the Investigator's responsibility to ensure that:

- All study products are accounted for and not used in any unauthorized manner
- All used foils and unused supplies are returned by each subject
- All unused products are available for return to the Study Sponsor, as directed
- Any study lenses associated with a device deficiency or with any product-related adverse event [ie, ADE or SADE] are returned to the Study Sponsor for investigation. Refer to Section 7.3 of this protocol for additional information on the reporting of device deficiencies and AEs and the return of study products associated with these events.

## 4.3 Worn Lens Collection, Storage and Return

Worn lenses will be returned to the Study Sponsor. Collection, storage and return instructions will be detailed in the CLY935-C007 MOP.

# 5 STUDY PROCEDURES AND ASSESSMENTS

## 5.1 Visits and Examinations

### 5.1.1 Visit 1 (Day 1) – Screen / Baseline / Lens 1: Dispense

1.	Explain the purpose and nature of the study, and have the subject read, sign, and date the IRB-approved informed consent document. Additionally, have the individual obtaining consent from the subject and a witness, if applicable, sign and date the informed consent document. Provide a photocopy of the signed document to the subject and place the original signed document in the subject's chart. After signing the ICF, a subject will be assigned a subject number by the EDC system. A signed informed consent document defines the point of enrollment.
----	---

2.	Obtain demographic information and medical history, including information on all medications used within the past 30 days. Include herbal therapies, vitamins, and all over-the-counter as well as prescription medications.
3.	Perform logMAR VA with habitual correction. 
 
• OD, OS, distance only, contact lenses
 
 Record habitual lens information (brand, power) and lens care information (brand).
	[REDACTED]
5.	Perform a manifest refraction.
6.	Perform logMAR BCVA with manifest refraction. 
 
• OD, OS, distance only
 
 Note: Distance BCVA must be 0.00 logMAR or better in each eye for the subject to qualify for the study.
7.	Perform slit-lamp biomicroscopy (without contact lenses) to evaluate the following: 
 
• Limbal hyperemia
 
• Bulbar hyperemia
 
• Corneal staining
 
• Conjunctival staining
 
• Palpebral conjunctival observations
 
• Corneal epithelial edema
 
• Corneal stromal edema
 
• Corneal vascularization
 
• Conjunctival compression/indentation
 
• Chemosis
 
• Corneal infiltrates
 
• Other findings
 

8.	Determine study lens powers based upon the manifest refraction and habitual lens powers.
9.	Review inclusion/exclusion criteria to determine if the subject qualifies to be randomized into the study. If subject qualifies, request randomization. If subject does not qualify, exit the subject from the study as a screen failure.
10.	Based upon the randomized treatment sequence, have the subject insert the appropriate Lens 1 study lenses, being careful to maintain the correct OD and OS lens assignments. [REDACTED] 
 
• Keep all lidding foils of lenses used during lens fit process for study lens accountability.
 
• Follow procedures to maintain masking.
 

11.	
Evaluate the study lenses by performing the following:
 

• logMAR VA with study lenses (OD and OS, at distance)*

 
*VA w/study lenses must be 20/25 in each eye or better for subject to leave the office

13.	
Assess and record any AEs and device deficiencies reported or observed during the study visit.
 
Note: AEs and device deficiencies must be recorded for all enrolled subjects from the time of signature of informed consent including those that screen fail.

14.	
Dispense study lenses, new lens case, and lens care solution.
 
Provide the subject with written and verbal instructions on lens wear and care.

16.	
Schedule Visit 2 to take place on study Lens 1 Day <math>8 \pm 2</math> days.
 
Note: Schedule Visit 2 at a time of day that allows a minimum of 6 hours of lens wear prior to visit.
 
Remind the subject of the following:
 

• To not use any lubricating drops during lens wear

• To wear the lenses at least 5 days a week and 8 hours per day

• To wear study lenses a minimum of 6 hours on the day of their follow-up study visit

### 5.1.2 Visit 2 (Day 8 ± 2 Days) – Lens 1: Week 1 Follow-up

1.	Obtain information on any changes in medical health and/or the use of concomitant medications.
2.	Record any device deficiencies or AEs, including those associated with changes in concomitant medication dosing, which are observed or reported since the previous visit.
	
[REDACTED]
 
[REDACTED]
 
[REDACTED]
 
Confirm subject has worn the study lenses for a minimum of 6 hours on the day of follow-up visit.

	[REDACTED]
5.	Evaluate the study lenses by performing the following: 

• logMAR VA with study lenses (OD and OS, at distance)

	
[REDACTED]
 
[REDACTED]
 
[REDACTED]
 
[REDACTED]
 
[REDACTED]
 
[REDACTED]

7.	Perform slit-lamp biomicroscopy (without contact lenses) to evaluate the following: 

• Limbal hyperemia

• Bulbar hyperemia

• Corneal staining

• Conjunctival staining

• Palpebral conjunctival observations

• Corneal epithelial edema

• Corneal stromal edema

• Corneal vascularization

• Conjunctival compression/indentation

• Chemosis

• Corneal infiltrates

• Other findings

	[REDACTED]
	[REDACTED]
9.	
Schedule Visit 3 to take place on study Lens 1 Day <math>30 \pm 2</math> days.
 
Note: Schedule Visit 3 at a time of day that allows a minimum of 6 hours of lens wear prior to visit.
 
Remind the subject of the following:
 

• To not use any lubricating drops during lens wear

• To wear the lenses at least 5 days a week and 8 hours per day

• To wear study lenses a minimum of 6 hours on the day of their follow-up study visit

 
[REDACTED]

	[REDACTED]

### 5.1.3 Visit 3 (Day $30 \pm 2$ Days) – Lens 1: Month 1 Follow-up. Lens 2: Dispense

1.	Obtain information on any changes in medical health and/or the use of concomitant medications.
2.	Record any device deficiencies or AEs, including those associated with changes in concomitant medication dosing, which are observed or reported since the previous visit(s).
	[REDACTED]
	[REDACTED]
	Confirm the subject has worn the study lenses for a minimum of 6 hours on the day of follow-up visit.
	[REDACTED]
5.	Evaluate the study lenses by performing the following: 

• logMAR VA with study lenses (OD and OS, at distance)

	
[REDACTED]
 
[REDACTED]
 
[REDACTED]
 
[REDACTED]
 
[REDACTED]
 
[REDACTED]
 
[REDACTED]

	
[REDACTED]
 
[REDACTED]
 
[REDACTED]

	
[REDACTED]

9.	
Perform slit-lamp biomicroscopy (without contact lenses) to evaluate the following:
 
 
• Limbal hyperemia
 
• Bulbar hyperemia
 
• Corneal staining
 
• Conjunctival staining
 
• Palpebral conjunctival observations
 
• Corneal epithelial edema
 
• Corneal stromal edema
 
• Corneal vascularization
 
• Conjunctival compression/indentation
 
• Chemosis
 
• Corneal infiltrates
 
• Other findings
 

10.	
Based upon the randomized treatment sequence, have the subject insert the appropriate study Lens 2, being careful to maintain the correct OD and OS lens assignments [REDACTED]
 
[REDACTED]
 
 
• Keep all lidding foils of lenses used during lens fit process for study lens accountability.
 
• Follow procedures to maintain masking.
 

11.	
Evaluate the study lenses by performing the following:
 
 
• logMAR VA with study lenses (OD and OS, at distance)*
 
 
*VA w/study lenses must be 20/25 in each eye or better for subject to leave the office

13.	Dispense study lenses, new lens case, and lens care solution. Provide the subject with written and verbal instructions on lens wear and care.
15.	
Schedule Visit 4 to take place on study Lens 2 Day <math>8 \pm 2</math> days.
 
Note: Schedule Visit 4 at a time of day that allows a minimum of 6 hours of lens wear prior to visit.
 
Remind the subject of the following:
 
 
• To not use any lubricating drops during lens wear
 
• To wear the lenses at least 5 days a week and 8 hours per day
 
• To wear study lenses a minimum of 6 hours on the day of their follow-up study visit
 

**5.1.4 Visit 4 (Day  $8 \pm 2$  Days) – Lens 2: Week 1 Follow-up**

1.	Obtain information on any changes in medical health and/or the use of concomitant medications.
2.	Record any device deficiencies or AEs, including those associated with changes in concomitant medication dosing, which are observed or reported since the previous visit.

	
[Redacted]
 
Confirm subject has worn the study lenses for a minimum of 6 hours on the day of follow-up visit.

	
[Redacted]

5.	Evaluate the study lenses by performing the following: 

• logMAR VA with study lenses (OD and OS, at distance)

	
[Redacted]

7.	Perform slit-lamp biomicroscopy (without contact lenses) to evaluate the following: 

• Limbal hyperemia

• Bulbar hyperemia

• Corneal staining

• Conjunctival staining

• Palpebral conjunctival observations

• Corneal epithelial edema

• Corneal stromal edema

• Corneal vascularization

• Conjunctival compression/indentation

• Chemosis

• Corneal infiltrates

• Other findings

	
[Redacted]

9.	
Schedule Visit 5 to take place on study Lens 2 Day 30 ± 2 days.
 
Note: Schedule Visit 5 at a time of day that allows a minimum of 6 hours of lens wear prior to visit.
 
Remind the subject of the following:
 
 
• To not use any lubricating drops during lens wear
 
• To wear the lenses at least 5 days a week and 8 hours per day
 
• To wear their study lenses a minimum of 6 hours on the day of their follow-up study visit
 
 
[REDACTED]

[REDACTED]	[REDACTED]

**5.1.5 Visit 5 (Day 30 ± 2 Days) – Lens 2: Month 1 Follow-up/Exit**

1.	Obtain information on any changes in medical health and/or the use of concomitant medications.
2.	Record any device deficiencies or AEs including those associated with changes in concomitant medication dosing, which are observed or reported since the previous visit.
[REDACTED]	[REDACTED]
[REDACTED]	Confirm subject has worn study lenses for a minimum of 6 hours on the day of follow-up visit.
[REDACTED]	[REDACTED]
5.	
Evaluate the study lenses by performing the following:
 
 
• logMAR VA with study lenses (OD and OS, at distance)
 

[figure not shown]
[REDACTED]	
[REDACTED]	
[REDACTED]	
[REDACTED]	
[REDACTED]	
[REDACTED]	
[REDACTED]	
[REDACTED]	
[REDACTED]	
10.	Perform slit-lamp biomicroscopy (without contact lenses) to evaluate the following: 

• Limbal hyperemia

• Bulbar hyperemia

• Corneal staining

• Conjunctival staining

• Palpebral conjunctival observations

• Corneal epithelial edema

• Corneal stromal edema

• Corneal vascularization

• Conjunctival compression/indentation

• Chemosis

• Corneal infiltrates

• Other findings

11.	Perform logMAR VA with habitual correction. 

• OD, OS, distance only, contact lenses

 [REDACTED]
12.	Exit the subject from the study.

[REDACTED]

[REDACTED]

[REDACTED]

[REDACTED]

## 5.2 Unscheduled Visits

Any visit that occurs between regularly scheduled visits is an Unscheduled Visit. If a subject requires an Unscheduled Visit, he/she must be advised to return to the office wearing the study lenses, if at all possible (unless he/she is experiencing a sign or symptom [as indicated in Section 3.3 Risks and Benefits]). During all unscheduled visits, the Investigator must conduct the following procedures:

- Collect AE and Device Deficiency information
- Assess and record changes in medical condition or concomitant medication
- Assess and record VAs
- Perform biomicroscopy (assessments with or without lenses, as possible)

In addition, all procedures for Visit 5 (Follow-up/Exit) should be completed (as possible). The Investigator may perform additional procedures for proper diagnosis and treatment of the subject. The Investigator must document this information in the subject's case history source documents.

If during an Unscheduled Visit the subject is discontinuing the study lenses or discontinuing from the study, the Investigator must conduct Exit procedures according to Table 1-1: Schedule of Study Procedures and Assessments, as possible.

## 5.3 Discontinued Subjects

Discontinued subjects are those who withdraw or are withdrawn from the study after signing the informed consent, including screen failures. Subjects may discontinue from the study at any time for any reason. Subjects may also be discontinued from the study at any time if, in the opinion of the Investigator, their continued participation poses a risk to their health. Discontinued subjects will not be replaced (ie, their subject numbers will not be re-assigned/re-used).

Should a subject exhibit any clinically relevant signs, symptoms, or other clinical observations that possibly could be associated with suspected sensitivity or intolerance to one of the study treatments, the Investigator must document those observations on an AE Form.

Any subject who exits early from the study (excluding screen failures) must undergo all procedures outlined at Visit 5, as applicable.

The Investigator must document the reason for study or treatment discontinuation in the subject's case history source documents.

To ensure the safety of all subjects who discontinue early, Investigators must assess each subject and, if necessary, advise them of any therapies and/or medical procedures that may be needed to maintain their health.

## **5.4 Clinical Study Termination**

The Study Sponsor reserves the right to close the investigational site or terminate the study in its entirety at any time, for reasonable cause.

If the clinical study is prematurely terminated or suspended by the Study Sponsor:

- The Study Sponsor must:
  - Immediately notify the Investigator(s) and subsequently provide instructions for study termination.
  - Inform the Investigator and the regulatory authorities of the termination/suspension and the reason(s) for the termination/suspension, as applicable.
- The Investigator must:
  - Promptly notify the IRB of the termination or suspension and of the reasons.
  - Provide subjects with recommendations for post-study treatment options as needed.

The Investigator may terminate a site's participation in the study for reasonable cause.

## 6 ANALYSIS PLAN

Continuous variables will be summarized using the number of observations, mean, standard deviation, median, minimum, and maximum. Categorical variables will be summarized with counts and percentages from each category.

Any deviations to this analysis plan will be updated during the course of the study as part of a protocol amendment or will be detailed in the clinical study report.

### 6.1 Subject Evaluability

The final subject evaluability will be determined prior to breaking the code for masked treatment (lens) sequence assignment and locking the database, based on the Deviations and Evaluability Plan.

### 6.2 Analysis Data Sets

#### 6.2.1 Safety Analysis Set

Safety analyses will be conducted using the safety analysis set on a treatment-emergent basis. As such, the safety analysis set will include all subjects/eyes exposed to any study lenses evaluated in this study. For treatment-emergent safety analyses, subjects/eyes will be categorized under the actual study lenses exposed.

### 6.3 Demographic and Baseline Characteristics

Demographic information (age, sex, ethnicity, race) will be summarized on the Safety Analysis Set. Baseline data pertaining to habitual lens (lens brand, lens care brand) and keratometry readings will be summarized on the Safety Analysis Set as well.

### 6.4 Effectiveness Analyses

This study defines 1 primary endpoint [REDACTED]. The Safety Analysis Set will be used for all effectiveness analyses.

#### 6.4.1 Primary Effectiveness

The primary objective of this study is to describe the clinical performance of an investigational silicone hydrogel contact lens over 30 days of daily wear. The primary endpoint is distance VA with study lenses, collected in logMAR, for each eye.

### 6.4.1.1 Statistical Hypotheses

No inferences are to be made on the primary effectiveness endpoint; therefore, no hypotheses are formulated.

### 6.4.1.2 Analysis Methods

Descriptive statistics will be presented.

[Redacted]

- | [Redacted]
- | [Redacted]
- | [Redacted]
- | [Redacted]
- | [Redacted]
- | [Redacted]
- | [Redacted]
- | [Redacted]
- | [Redacted]
- | [Redacted]
- | [Redacted]
- | [Redacted]
- | [Redacted]

[Redacted]

[Redacted]

[Redacted]

## 6.5 Subgroup Analyses

It is not expected that demographic or baseline characteristics will have an impact on the study results in this study. No subgroup analyses are planned.

## 6.6 Handling of Missing Data

All data obtained in evaluable subjects/eyes will be included in the analysis. No imputation for missing values will be carried out.

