§ Subjects are required to wear the study lenses for a minimum of 6 hours on the day of follow-up visits prior to the visit.

[REDACTED]

Printed By:

Print Date:

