## 4.3 Statistical Methods for Effectiveness Analyses

### 4.3.1 Primary Effectiveness Analyses

Descriptive statistics (number of observations, mean, standard deviation, median, minimum, maximum) for the logMAR values will be presented.

[Redacted]

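### Does the undefined word evaluable leave it unclear which eyes and visits enter the visual acuity summary?

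*Protocol*

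**What the plan says.** Protocol 6.2.1 and SAP 2.1 define a single set: "the safety analysis set will include all subjects/eyes exposed to any study lenses evaluated in this study". Protocol 6.4 then says "The Safety Analysis Set will be used for all effectiveness analyses", and SAP 4 agrees. On missing data, Protocol 6.6 and SAP 4 both say "All data obtained in evaluable subjects/eyes will be included in the analysis" and rule out imputation.

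Protocol 6.1 says "The final subject evaluability will be determined prior to breaking the code" and before database lock, on the basis of a Deviations and Evaluability Plan. That plan was not among the documents reviewed, and the visible SAP does not cite it.

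Two conduct rules bear on the primary endpoint, per-eye distance VA with study lenses:

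- **Dispensing.** At Visit 1, step 9 reads "If subject qualifies, request randomization", step 10 is lens insertion, and step 11 carries the note "VA w/study lenses must be 20/25 in each eye or better for subject to leave the office". Visit 3 repeats the note for Lens 2.
- **Follow-up.** The footnote to Table 1-1 reads "Subjects are required to wear the study lenses for a minimum of 6 hours on the day of follow-up visits prior to the visit", and the visits have a window of ±2 days.

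The analysis is in SAP 4.3.1: "Descriptive statistics (number of observations, mean, standard deviation, median, minimum, maximum) for the logMAR values will be presented".

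**The concern.** If evaluable means no more than being in the Safety Analysis Set, the word is redundant and the step in Protocol 6.1 has no stated use. If it means more, an unstated filter acts on the primary endpoint. The level also shifts: 6.1 speaks of subjects, 6.6 of subjects or eyes, and neither of visits.

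The order of steps at Visit 1 makes the question concrete. A subject is randomized and wears the lens before VA with it is measured. An eye that cannot reach 20/25 is thus already exposed, belongs to the set, and has a poor value on the endpoint. Removing it would select on the outcome that the study sets out to describe. In a descriptive study the n, mean, SD and range are the result, so the rule for which values enter them deserves care. The 6-hour rule and the visit window raise a similar question, with no stated consequence for the analysis when they are missed.

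**Working it through.** **1. Reading the sections together.** Protocol 6.4 fixes the population for effectiveness as the exposure set. Protocol 6.6 comes under missing data: it says that observed data are used and gaps are not filled. Read this way, the two sections agree. The table includes all recorded values from exposed eyes, and missing values stay missing.

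**2. Applying that reading.**

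| Case | In the exposure set? | Visible text removing the value? | Result |
|---|---|---|---|
| Eye below 20/25 at dispensing | Yes, the lens was worn | None; the note governs leaving the office | Kept |
| Follow-up with under 6 hours of wear | Yes | None; sites confirm the wear time | Kept |
| Follow-up outside ±2 days | Yes | None | Kept |

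**3. How many values could be in doubt at dispensing.** Study-lens VA is scheduled 6 times per eye: Visits 1, 2, 3 (follow-up), 3 (dispensing), 4 and 5. Two of these are dispensing and four are follow-up. For 32 completers (64 eyes) that is 64 × 2 = 128 dispensing and 64 × 4 = 256 follow-up values. These are totals and do not count values in doubt. A completer has left the office with both lenses, so under the rule the final dispensing values of completers are all 20/25 or better. The dispensing question concerns exposed subjects who do not complete. The planned allowance is about 36 − 32 = 4 subjects, and Protocol 3.4 counts screening failures in it.

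**4. Size at dispensing.** 20/25 is log10(25/20) = 0.097 logMAR. Suppose k of n eyes miss the rule with value b, and the other eyes average m. Keeping rather than dropping them moves the mean by k(b − m)/n. The values of b and m, and an SD of 0.08 in the passing eyes, are assumptions; the documents give none.

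| Case (m = 0.00) | Shift in mean | SD if kept |
|---|---|---|
| One subject, k = 2, n = 72, b = 0.20 | 2 × 0.20 / 72 = 0.0056 | 0.0855 |
| One subject, k = 2, n = 64, b = 0.20 | 2 × 0.20 / 64 = 0.0063 | 0.0862 |
| Two subjects, k = 4, n = 64, b = 0.30 | 4 × 0.30 / 64 = 0.0188 | 0.1065 |
| Whole allowance, same lens, k = 8, n = 72, b = 0.20 | 8 × 0.20 / 72 = 0.0222 | not computed |

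The maximum is the sensitive statistic: at most 0.097 if such eyes are dropped, and b if one is kept. The last row is an extreme, since it has every planned non-completer failing on the same lens. Entry criteria make even one failure unlikely: best-corrected VA of 0.0 logMAR or better in each eye, cylinder of at most 0.75 D, and lens powers chosen from the refraction and the habitual lenses.

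**5. Follow-up rule.** If 5%, 10% or 20% of eyes at a visit fell short of 6 hours (assumed), 3.2, 6.4 or 12.8 of 64 eyes would be affected. The mean would move by that fraction times the VA difference between short and full wear. The documents give no such difference, so no size can be stated.

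**The case for a change.** The best case for a change is that it would cost one sentence in each of three places. A cross-reference, or the words Safety Analysis Set in place of evaluable, would tell a reader exactly which eyes produced the table. A filter on 20/25 would select on the endpoint, and Protocol 8.2 leaves investigators unmasked, so settling evaluability before the code is broken is only partial protection. The listings and tables in SAP 3 on exclusions, discontinuations and subject accounting are organized by subject and may not explain a missing eye or visit.

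Part of this stands. The visible documents give no criteria for evaluable, and the visible SAP does not point to the companion plan. But a filter on 20/25 is only a possibility; nothing visible describes one. Calling the term undefined also goes too far, since Protocol 6.1 assigns evaluability to a named plan. The text is redacted around the lens-fitting steps at Visits 1 and 3 and in both effectiveness sections, so silence there proves little. Section 6 of the protocol requires departures from the analysis plan to be handled by amendment or detailed in the study report. Replacing the word without sight of the companion plan could also create a conflict that does not now exist.

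**Conclusion.** The concern does not call for a change. An analyst who follows the protocol and SAP would summarize all recorded VA values from all exposed eyes, which is also the choice that avoids selecting on the outcome. If the companion plan does remove some subjects, that is settled before the code is broken, and SAP 3 provides a listing of excluded subjects.

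Under the assumptions shown, one affected subject moves a dispensing mean by about 0.006 logMAR. The maximum could change visibly, but only if a subject misses 20/25 and is then dropped. There is no primary hypothesis (Protocol 6.4.1.1, SAP 4.2) and no decision criterion (SAP Executive Summary), so no test or success decision depends on it. A cross-reference to the Deviations and Evaluability Plan would be tidy, as an editorial matter only.

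This rests on two conditions: that evaluable adds no outcome-based exclusion, and that the redacted text and the companion plan do not contradict the visible sections. Neither can be checked from the documents at hand.
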